- f. *Serious, suspected adverse reaction*. A suspected adverse reaction is considered “serious” if, in the view of the Investigator (i.e., the study site principal investigator) or Sponsor, it results in any of the following outcomes: death, a life-threatening adverse reaction, inpatient hospitalization or prolongation of existing hospitalization, a persistent or significant incapacity or substantial disruption of the ability to conduct normal life functions, or a congenital anomaly/birth defect.
- g. *Reportable non-compliance* refers to a failure on the part of the investigator or study team member to follow the terms of the IRB approved protocol or abide by applicable laws or regulations, that adversely affect the rights and welfare of subjects or significantly compromises the quality of the research data. Incidents of non-compliance on the part of the subject are not considered reportable.
- h. *Unanticipated Problem Involving Risk to Subjects or Others (UPIRTSO)* refers to any accident, experience, or outcome that meets the following criteria: unexpected in terms of nature, severity or frequency; related, or possibly related, to a subject’s participation in research; and places subjects or others at greater risk of harm (including physical, economic, or social) than was previously known or recognized.

Assessing and Reporting Adverse Events (AEs) and Non-compliance: Adverse events will be reviewed by the study sites and assessed for relationship to the study intervention. Investigators and study team will determine if any related adverse events occur during the period from

enrollment through study participation termination. If reportable adverse events occur, they will be recorded on the adverse event case report form in the electronic data capture system, which will be submitted to the Coordinating Center. All reported adverse events will be classified by: a) Severity (fatal or life-threatening, serious, or non-serious); and b) Expected vs. Unexpected. Please refer to the table below for timelines for reporting.

This study population is expected to have a large number of serious adverse events, including death from trauma related injuries. Expected adverse events that are related or possibly related to the intervention will be documented and reviewed for changes in nature, severity, or frequency across the study population.

Organization	Unexpected, fatal or life-threatening, suspected adverse reactions	Unexpected, serious, suspected adverse reactions	Expected adverse reactions	Reportable non-compliance	UPIRTSO
IRB	24 hours	10 working days	No reporting	10 working days	10 working days
FDA	7 calendar days	15 calendar days	No reporting	No requirement	No requirement
Dept of Defense	30 calendar days	30 calendar days	No reporting	30 calendar days**	30 calendar days*
DSMB	24 hours	7 calendar days	At next meeting (every 6 months)	At next meeting (every 6 months)	14 days*

*reported based on IRB determination that event is UPIRTSO

**reported based on IRB determination that non-compliance is serious or continuing

Data Safety Monitoring Board (DSMB): A Data and Safety Monitoring Board (DSMB) will be created to review this study and provide recommendations re. study continuation to the IND Sponsor. After initial approval and at periodic intervals (to be determined by the committee) during the course of the study, the DSMB responsibilities are to:

- a. Review the research protocol, informed consent documents and plans for data and safety monitoring;
- b. Evaluate the progress of the study, including periodic assessments of data quality and timeliness, participant recruitment, accrual and retention, participant risk versus benefit, adverse events, unanticipated problems, performance of the trial sites, and other factors that can affect study outcome;
- c. Consider factors external to the study when relevant information becomes available, such as scientific or therapeutic developments that may have an impact on the safety of the

participants or the ethics of the study;

- d. Review clinical center performance, make recommendations and assist in the resolution of problems reported by the IND Sponsor or study site Investigators;
- e. Protect the safety of the study participants;
- f. Report on the safety and progress of the study;
- g. Make recommendations to the IND Sponsor, and if required, to the FDA concerning continuation, termination or other modifications of the study based on the observed beneficial or adverse effects of the treatment under study;
- h. Monitor the confidentiality of the study data and the results of monitoring;
- i. Assist the IND Sponsor by commenting on any problems with study conduct, enrollment, sample size and/or data collection.
- j. The DSMB will include experts in emergency medicine, surgery (trauma/critical medicine), bioethics and biostatistics. Members will consist of persons independent of the investigators who have no financial, scientific, or other conflict of interest with the study. Written documentation attesting to absence of conflict of interest will be required.
- k. The University of Pittsburgh Office of Clinical Research, Health Sciences will provide the logistical management and support of the DSMB. A safety officer (chairperson) will be identified at the first meeting. This person will be the contact person for serious adverse event reporting. Procedures for this will be discussed at the first meeting.
- l. The first meeting will take place before initiation of the study to discuss the protocol, approve the commencement of the study, and to establish guidelines to monitor the study. The follow-up meeting frequency of the DSMB will be determined during the first meeting. An emergency meeting of the DSMB will be called at any time by the Chairperson should questions of patient safety arise.

XI. Quality Control, Assurance and Confidentiality

Protocol Compliance: The participating study site Investigators will not deviate from the protocol for any reason without prior written approval from the IRB except in the event of the safety of the research subject. In that event, the study site Investigator will notify the IND Sponsor and reviewing IRB immediately, if possible, and request approval of the protocol deviation, or, if prospective IND Sponsor and IRB approval is not possible, the study site Investigator will notify the IND Sponsor and reviewing IRB promptly following the respective protocol deviation. The study site Investigator will inform the reviewing IRB of all protocol deviations and unanticipated events involving risks to the research subjects and others and will obtain prospective IRB approval for all proposed protocol changes. Persistent or serious noncompliance may result in termination of the study site's participation in the research study.

Protocol Deviations: Due to the relative focused inclusion criteria and the short intervention period, we expect few protocol deviations as compared to other large multicenter trials. If monitoring reports demonstrate evidence of continuing protocol deviations, we will analyze them to determine if they are site specific or common across the study. We will note if specific inclusion or exclusion criteria are being misinterpreted, if a certain time point in testing is being omitted, or if a common set of data elements are missing. If the deviations are site specific, retraining will be done at the site. If the problems are study wide, we will discuss them with the

[figure not shown]
other investigators, the DOD and the FDA to see if the protocol needs to be amended or recruitment put on hold.

Privacy and Confidentiality: The study site Investigators and members of their research team will make reasonable effort to ensure the research subjects' confidentiality. Subject name and other identifiable information will be kept in a secure, locked, limited access area.

Investigator Responsibilities:

The study site Investigators will agree to implement the IRB approved protocol and conduct the study in accordance with Section 9 (Commitments) of Form FDA 1572, 21 CFR Part 312, Subpart D, and the ICH GCP Guidelines (E6, Section 5) as well as all applicable national, state and local laws. The study will be performed in accordance with ethical principles that have their origin in the Declaration of Helsinki and are consistent with ICH/Good Clinical Practice, and applicable regulatory requirements.

Timetable

XII. References

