Secondary Outcomes: *Our principal secondary outcome for the trial will be age of whole blood and its association with all primary and additional secondary outcomes.* Additional secondary outcomes for the proposal will include 3-hour mortality, 6-hour mortality, 24-hour mortality, in hospital mortality, death from hemorrhage, death from brain injury, blood and blood component transfusion requirements in the initial 24 hours, incidence of Multiple Organ Failure (MOF), incidence of nosocomial infection, incidence of acute respiratory distress syndrome (ARDS), time to hemostasis, incidence of coagulopathy by TEG, incidence of allergic/transfusion reaction and measurements of platelet and overall patient hemostatic function.

Secondary Outcome Definitions:

Age of whole blood: Age of the LTWB O blood products transfused will be recorded as designated by the respective blood banking service at each respective site from the time of donation. Based upon the separation procedures utilized at the respective blood bank, LTWB O units will have a defined maximum shelf life out to 21 days or 35 days.

Specific sites may have the capability to recycle LTWB O units to packed red blood cells and standard site-specific protocols will be utilized for this. When the age of 2 units of LTWB O are disparate, an average age of LTWB O transfusion will be calculated. We will stratify Age of LTWB O into YOUNG (1-14 days) and OLD (>14 days). We will similarly bin age or average age of LTWB O by week (1-7days), (8-14days), (15-21days), (22-28days), and > 28 days and allow comparison across all primary and secondary outcomes.

3-hour, 6-hour, 24-hour, and In-hospital mortality: 3-hour, 6-hour, 24-hour, and in hospital mortality will be recorded from the time of randomization. Over the first

24 hours, we will document and record the time of death in hours, while after the 24-hour time period, we will document and record the time of death in days from arrival. We suspect that patients in hemorrhagic shock will have a significant percentage of mortality occurring in the first 24-hour period.

Time to death: Time to death will be based on the documented and recorded time of death in days from arrival. Those surviving up to 30-days post enrollment will be censored.

Mortality from hemorrhage and brain injury: Cause of death will be adjudicated by a site investigator

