Twenty four-hour blood and blood component transfusion requirements: 24-hour blood and blood component transfusion requirements will be determined by recording the type of product, the number of units transfused, and the time of transfusion. Any initiation of blood transfusion will be considered completed.

Multiple Organ Failure (MOF): Organ dysfunction will be evaluated via the Denver Post-injury Multiple Organ Failure Score, a well-validated scoring system in injured patients and characterized as an incidence rate (%) and as MOF free days.^{14,15} Patients who are never admitted to the ICU or those with a length of ICU stay of less than 48 hours will be considered to have a Denver score of 0. A summary of the Denver score may be calculated by summing the worst scores of each of the individual systems. A summary Denver score > 3 will be classified as MOF. Scores will be determined daily up until Day 7 or ICU discharge, whichever comes first.¹⁵

Nosocomial Infection (NI): The CDC criteria for the diagnosis of hospital acquired pneumonia and blood stream infection will be utilized (www.cdc.gov/nhsn) and recorded over 30 days.

Acute Respiratory Distress Syndrome (ARDS): The Berlin definition for mild ARDS ($\text{PaO}_2/\text{FIO}_2, \leq 300 \text{ mm Hg}$ + timing, imaging and origin criteria) will be utilized as a threshold value to determine the incidence of ARDS and will be further stratified into Moderate ($\text{PaO}_2/\text{FIO}_2, \leq 200 \text{ mm Hg}$) and Severe ($\text{PaO}_2/\text{FIO}_2, \leq 100 \text{ mm Hg}$).¹⁶

Coagulation parameters: During the first 60 minutes from arrival to the TOWAR trial site, blood for PT, INR and point of care rapid-TEG or conventional TEG analysis will be obtained. These measurements will be repeated as close to 24 hours (+/- 12 hours) from the time of arrival as feasible, to coordinate with other lab draws and staffing patterns. For those sites with rapid TEG capabilities, tissue factor will be added to a citrated whole blood collection tube and rapid TEG parameters including activated clotting time (ACT, seconds or R time), angle (α , degrees), coagulation time (K, seconds), maximum amplitude (MA, mm), clot strength (G, dynes/cm²), and estimated percent lysis (LY30, %) will be measured for each patient.

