A similar approach will be taken for the secondary outcomes, though the analytic approach may vary based on the distribution of the outcome. For example, for a continuous secondary outcome (e.g., clotting time parameters); a mixed-effects linear regression model to estimate the independent effect of the age of whole blood on the outcome. For time to event outcomes (e.g., time to death), Kaplan-Meier curves will be generated for each treatment group and a log-rank test will be used to compare the distribution of the cumulative proportion. Observations will be censored at 30 days after arrival. A multivariable analysis of survival with the use of a Cox

proportional-hazard with shared frailty model to evaluate the treatment effect with adjustment for possible confounding factors and site clustering on survival.

AIM#3 Analysis: Determine whether prehospital low titer whole blood as compared to standard prehospital resuscitation results in lower early mortality endpoints, blood and blood component transfusion requirements, lower incidence of coagulopathy, and improved hemostatic and platelet function in patients at risk of hemorrhagic shock.

The analysis of the secondary outcome will mirror the analytic approach for Aim 2. The analytic approach for other binary outcomes (e.g., 6-hour mortality) will be identical as those for the primary analysis. For continuous outcomes (e.g., 24-hour blood and component transfusion requirements), a mixed effect regression model will be used to determine if the average number of units transfused between the two treatment groups differ. For time to event outcomes (e.g., time to hemostasis), Kaplan-Meier curves will be generated for each treatment group and a log-rank test will be used to compare the distribution of the cumulative proportion. A multivariable analysis of survival with the use of a Cox proportional-hazard with shared frailty model to evaluate the treatment effect with adjustment for possible confounding factors and site clustering on survival.

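### The Denver score-0 rule makes no exception for death, so MOF incidence needs a competing-event label and MOF-free days needs a window and a rule for deaths (minor, secondary outcome only)

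*Combined protocol and SAP*

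**What the plan says.** Section III (Outcomes, Multiple Organ Failure) classes a summary Denver score above 3 as MOF and has it "characterized as an incidence rate (%) and as MOF free days". Two groups are given a score without assessment: "Patients who are never admitted to the ICU", and "those with a length of ICU stay of less than 48 hours will be considered to have a Denver score of 0". Neither group is limited to patients who are alive. On timing: "Scores will be determined daily up until Day 7 or ICU discharge, whichever comes first". Death is not named as an end of scoring. No formula, denominator or value for deaths is given for MOF-free days.

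The mortality definitions in the same section expect many early deaths: "We suspect that patients in hemorrhagic shock will have a significant percentage of mortality occurring in the first 24-hour period". For the first 24 hours, "we will document and record the time of death in hours"; later deaths are recorded in days.

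MOF incidence is a listed secondary outcome and also enters the blood-age comparison: "Our principal secondary outcome for the trial will be age of whole blood and its association with all primary and additional secondary outcomes". In section VI (AIM#3 Analysis), "The analytic approach for other binary outcomes (e.g., 6-hour mortality) will be identical as those for the primary analysis". The Missing Data paragraph addresses imputation of the primary outcome. It would not reach these patients in any case, because they hold an assigned score and are not missing.

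**The concern.** A score of 0 gives the same value to two opposite courses: patients well enough to avoid or leave the ICU, and patients who died before organ failure could be observed. The trial expects many deaths in that period. Section II also reports that, in the earlier prehospital plasma trial, survival separated within the first 3 hours. If LTWB works early, more of its patients live long enough to be scored, and some of them develop MOF. The incidence comparison then leans against the arm with fewer early deaths. The same would hold for younger blood if it lowered early mortality. If early mortality is equal, there is no effect.

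For MOF-free days the difficulty is different. The value given to a death can decide which way the comparison points, and that value is not stated. In an open-label trial it should be fixed before outcome data are seen.

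**Working it through.** **Inputs from the plan (Sample Size Justification).** 30-day mortality 26% vs 16%; 340 standard care and 680 LTWB. Blood age: mortality 22.6% (old) vs 14% (young); 40% and 60% of 680 give 272 and 408.

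The plan gives no MOF figure to reproduce. Its sample size, the source of the mortality inputs, does reproduce. Two proportions at 26% vs 16% need 260 per arm (256.5 with unpooled variance). Applying n(1 - ICC)/(1 - n x ICC/20), with 20 services per arm and ICC 0.02, gives 344 (338 unpooled) against the stated 340.

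**Assumptions (not in the documents).**
- f, the share of deaths falling under the score-0 rule: 0.5 (range 0.3-0.7).
- r, the MOF risk in the other patients: 0.25 (range 0.15-0.25).
- k, the multiple of that risk in rescued patients, meaning those who would have died early in the higher-mortality group: 1 or 2.
- d, MOF days per case in a 7-day window: 4 (range 3-7).

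Standard errors ignore clustering. Deaths from 48 hours to day 7 are not modelled.

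**Step 1: early deaths, e = f x mortality.** Standard care 0.5 x 0.26 = 0.13 (about 44 of 340). LTWB 0.5 x 0.16 = 0.08 (about 54 of 680).

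**Step 2: coded MOF incidence.** Higher-mortality group: (1 - e_hi) x r. Lower-mortality group: that value + (e_hi - e_lo) x k x r. SE = square root of the sum of p(1 - p)/n over the two groups.

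| | Higher mortality | Lower mortality | Difference | SE | Ratio |
|---|---|---|---|---|---|
| Arms, k = 1 | 0.87 x 0.25 = 21.75% | 21.75% + 0.05 x 0.25 = 23.00% | 1.25 points | 2.76 | 0.45 |
| Arms, k = 2 | 21.75% | 24.25% | 2.50 points | 2.78 | 0.90 |
| Blood age, k = 1 | 22.18% | 23.25% | 1.08 points | 3.27 | 0.33 |
| Blood age, k = 2 | 22.18% | 24.33% | 2.15 points | 3.29 | 0.65 |

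Over the ranges of f, r and k, the lean is 0.45-3.50 points (0.20-1.28 SE) between arms and 0.39-3.01 points (0.14-0.93 SE) for blood age.

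**Step 3: MOF or early death, coded MOF + e.** Standard care 21.75% + 13% = 34.75%. LTWB 23.00% + 8% = 31.00% (k = 1), or 24.25% + 8% = 32.25% (k = 2). This points the other way from incidence alone.

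**Step 4: mean MOF-free days, arms, d = 4, k = 1.**
- Score 0 carried over 7 days, 7 - MOF x d: 7 - 0.2175 x 4 = 6.13 standard care; 7 - 0.23 x 4 = 6.08 LTWB. LTWB minus standard care: -0.05 (SE 0.110).
- Early deaths given 0, subtract a further 7e: 6.13 - 0.91 = 5.22; 6.08 - 0.56 = 5.52. Difference: +0.30 (SE 0.166).

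The gap between the two definitions is 7 x (0.13 - 0.08) = 0.35 days, or 0.21-0.49 over f = 0.3-0.7. With f = 0.5 and r = 0.25, over d = 3-7 and k = 1-2, the first definition gives -0.04 to -0.18 and the second +0.18 to +0.31. With deaths at 0 the difference equals (e_hi - e_lo)(7 - k x r x d). It is therefore positive whenever k x r x d is below 7; the largest value considered is 2 x 0.25 x 7 = 3.5. For blood age the same steps give -0.03 to -0.15 and +0.15 to +0.27, with a gap of 0.30.

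**The case against.** Incidence over all randomised patients, with deaths counted as non-cases, is a recognised quantity. Rescued patients who develop MOF are real cases, and the lean is under 1 SE in the base case. Mortality at 3, 6 and 24 hours, in hospital and at 30 days is already an outcome, so a careful reader has the companion information. Nowhere do the documents present MOF incidence as isolated organ benefit, and Aim 3 does not name MOF. All of this stands. It reduces the incidence issue to a label and a companion measure.

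A reader might infer that the plan rewards early death with a full 7 MOF-free days. The text does not establish that. It defines a score, not a day count, so the inference needs a fixed 7-day denominator and days dead counted as free, neither of which is stated. A days-alive reading is equally open. The papers cited for the score and the scoring window may contain a rule, but they cannot be checked from the documents.

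A reader might also take the 0.35 days as a bias, or conclude that the same data could be reported convincingly for or against LTWB. Neither is supported. The 0.35 days is the assumed early-mortality difference multiplied by 7. The -0.05 is only 0.45 of its SE.

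What does not fall away is the written rule: score 0 without an exception for death, followed by a day-based measure with no stated treatment of deaths.

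**Conclusion.** The point holds as a minor one. Taken as written, early deaths count as free of MOF. Incidence remains valid if it is labelled as having death as a competing event and is read beside mortality. Its lean is about 1.3 points in the base illustration and 2.5 with doubled risk in rescued patients. MOF-free days is undefined in a way that matters: over the ranges considered, its sign depends on whether early deaths keep the full window or receive 0.

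The sizes rest on the planned mortality differences and on assumed values for the early-death share, MOF risk, rescued-patient risk and days lost. They illustrate direction and scale only. They are not an exact forecast of the proposed definition either, which also gives 0 to deaths between 48 hours and day 7. The primary outcome of 30-day mortality is untouched.

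**What to change.** Amend the MOF definition and the SAP as follows.

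1. Restrict the score-0 rule to patients who leave the ICU alive before 48 hours, or who never need the ICU and survive to day 7.
2. Keep all randomised patients in the denominator. Count early deaths as a separate competing-event category; do not exclude them, since exclusion would condition the comparison on survival after randomisation.
3. Label MOF incidence as incidence with death as a competing event.
4. Define MOF-free days as days alive and free of MOF over days 1-7, with 0 for any death within that window.
5. Report MOF-or-death through day 7, with its components, beside MOF incidence for both the treatment-arm and the blood-age comparisons.

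The cost is wording and a little programming. Daily organ dysfunction scores, ICU days and time of death are already to be collected. The downside is that the composite and the 0-day rule are partly driven by mortality, so they should supplement MOF incidence and not replace it.
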